1. PROTOCOL SUMMARY

Study Title & ID	The Philips ICE Registry Protocol ID: IGT_IGD_ICE Registry Study_2019_10745
Project Name	“Philips ICE Registry”
Study Description	The purpose of this observational registry is to report real-world safety and performance of VeriSight for ultrasound guided ICE imaging in percutaneous cardiac intervention procedures when used in standard clinical practice.
Study Design	Prospective, multicenter, observational, single-arm registry
Primary Analyses	
Technical success – defined as successful delivery of VeriSight to the target intracardiac position and sustained device operation during the procedure
 
Imaging success – Adequate image quality as determined by the investigator.
 
Clinical success – Adequacy of VeriSight imaging for visualization of major cardiac structures, and guiding procedural intervention, and ability to detect/ assess intra-procedural complications.
 
Safety – Device-related adverse events periprocedural through discharge or ≤48 hours post-procedure, whichever is earlier.

Secondary Analyses	
 1. Procedural characterization when using VeriSight 2. Device characterization when using VeriSight 3. Physician survey regarding the Philips ICE system 4. Staff survey regarding the Philips ICE system

Document ID:	IGT_IGD_ICE Registry Study_2019_10745	Document title:		Classification:	Confidential
Modified:	24 APR 2021	Philips ICE Registry			
Version:	2.0	User Tool ID:	16.2.6UserTool0004	Page:	8
Status:	Final	User Tool Version Date	30May2019		

Clinical Registry Protocol
IGT_IGD_ICE Registry Study_2019_10745

Patient Population	
Inclusion Criteria
 
 • ≥18 years of age and willing to provide written, signed and dated, informed consent. • Scheduled for a procedure that is within the scope of clinical indications for VeriSight, per Instructions for Use (IFU) 
Exclusion Criteria
 
 • Contraindicated for ICE catheter placement or patient considerations that make placement of VeriSight not technically feasible • If alternate access (as needed instead of femoral) is not viable. • Known contraindicated conditions include sepsis, major coagulation abnormalities, presence of any intracardiac thrombus, presence of class IV angina or heart failure, deep vein thrombosis, or significant peripheral vascular disease.
Planned Enrollment	Up to 200 patients scheduled to undergo cardiac interventional percutaneous procedures for which ICE is indicated. Interim analysis is planned after the 100 th patient before further continuity of enrollment in the registry.
Registry Sites	Up to 10 sites in the United States with a maximum enrollment of no more than 30% patients at each participating site
Registry Exit	Either at discharge or ≤48 hours post-procedure, whichever is earlier
Registry Duration	Duration of the registry is estimated to be approximately 24 – 36 months.
Statistical Methodology	No hypothesis testing is planned. All subjects enrolled in the study will be accounted for in the study report. Descriptive statistics and 95% confidence intervals will be calculated for variables.

Document ID:	IGT_IGD_ICE Registry Study_2019_10745	Document title:	Classification:	Confidential	
Modified:	24 APR 2021	Philips ICE Registry			
Version:	2.0	User Tool ID:	16.2.6UserTool0004	Page:	9
Status:	Final	User Tool Version Date	30May2019		

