3. REGISTRY DESIGN

3.1. General Description

This is a prospective, multi-center, observational, single-arm registry intended to gather real-world data to report VeriSight ICE catheter performance and safety. It will be conducted in the United States under the approval of one or more recognized institutional review boards and in compliance with GCP guidelines defined in ISO:14155:2011, the Declaration of Helsinki, and all applicable federal and local laws and regulations. Only on label uses of the VeriSight ICE catheter will be allowed. No specific claims are being validated during this registry, though data analyzed from this protocol are intended to inform of future claims regarding the performance and safety of the VeriSight catheter.

Document ID:	IGT_IGD_ICE Registry Study 2019 10745	Document title:		Classification:	Confidential
Modified:	24 APR 2021	Philips ICE Registry			
Version:	2.0	User Tool ID:	16.2.6UserTool0004		
Status:	Final	User Tool Version Date	30May2019	Page:	14

Clinical Registry Protocol
IGT_IGD_ICE Registry Study_2019_10745

Enrolled patients will be imaged with VeriSight for various types of percutaneous cardiac interventional procedures. Enrolled subjects will be followed until discharge or ≤48 hrs post-procedure. The registry has a planned duration of approximately 24-36 months with interim analysis planned at 100 patients before further enrollment will be considered. Statistical hypotheses are not intended for this registry and descriptive analysis will be conducted. Data from all clinical sites are intended to be pooled for analysis. It is possible that sub-analyses may be conducted to demonstrate VeriSight guidance for target intervention types in structural heart and electrophysiology procedures.

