4.2. Exclusion Criteria

Patients who have ANY of the following exclusion criteria are NOT eligible for participation on the registry.

1. Contraindicated for ICE catheter placement or patient considerations that make placement of VeriSight not technically feasible
2. If alternate access (as needed instead of femoral) is not viable
3. Known contraindicated conditions include sepsis, major coagulation abnormalities, presence of any intracardiac thrombus, presence of class IV angina or heart failure, deep vein thrombosis, or significant peripheral vascular disease.

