4.4. Enrollment

Subjects who sign the informed consent form and are indicated for treatment procedure per VeriSight commercial labeling will be considered for the registry. A subject is considered enrolled in the registry when VeriSight has been placed in their vasculature and the device is switched “ON”. Participation is complete at discharge or ≤48 hours post-procedure from the registry site, whichever occurs first.

Document ID:	IGT_IGD_ICE Registry Study 2019 10745	Document title:		Classification:	Confidential
Modified:	24 APR 2021	Philips ICE Registry			
Version:	2.0	User Tool ID:	16.2.6UserTool0004	Page:	17
Status:	Final	User Tool Version Date	30May2019		

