4.5. Screen Failures

Only consented subjects who are considered enrolled in the registry will be followed. Those who provide consent, but then are determined to be ineligible at the time of enrollment will be considered screen failures.

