6.2. Schedule of Activities (SOA)

Table 1 provides an overview of registry procedures per visit.

Document ID:	IGT_IGD_ICE Registry Study_2019_10745	Document title:		Classification:	Confidential
Modified:	24 APR 2021	Philips ICE Registry			
Version:	2.0	User Tool ID:	16.2.6UserTool0004	Page:	19
Status:	Final	User Tool Version Date	30May2019		

Clinical Registry Protocol
IGT_IGD_ICE Registry Study_2019_10745

Table 1. Overview of registry procedure			
Procedures	Screening*	Index procedure	Post-Procedure (at discharge or 48hrs)
Assessment of eligibility	X		
Informed consent	X		
Record demographics	X		
Medical History and Physical (H&P)	X		
Record any baseline diagnostic imaging		X	
ICE imaging with VeriSight		X	
Image grading		X	
Procedural workflow and details		X	
Adverse device effects related to VeriSight		X	X
Registry exit			X
Usability assessment	Aggregate input		
Physical attributes of catheter	After 1 st patient enrolled	After 10 th patient enrolled	After last patient enrolled
Physician and staff survey	After 1 st patient enrolled	After 10 th patient enrolled	After last patient enrolled

*up to 30 days prior to index

Below are the brief study procedure steps.

- Subjects are evaluated for eligibility based on the inclusion and exclusion criteria
- Record demographics of subjects: age, gender, height, weight, ethnicity/race (if applicable)
- Record relevant medical and surgical histories
- The subjects will be imaged using the VeriSight device according to the routine workflows
- Relevant imaging for each procedural steps will be recorded.
- The Investigator will grade the imaging recorded
- The corresponding clinical information and information about the use of device and system, including device deficiencies and safety-related adverse device effects related to VeriSight, will be recorded by the Investigator in the CRF
- The registry examinations including all collected de-identified images will be transferred to Philips

Document ID:	IGT_IGD_ICE Registry Study_2019_10745	Document title:		Classification:	Confidential
Modified:	24 APR 2021	Philips ICE Registry			
Version:	2.0	User Tool ID:	16.2.6UserTool0004	Page:	20
Status:	Final	User Tool Version Date	30May2019		

Clinical Registry Protocol
IGT_IGD_ICE Registry Study_2019_10745

- After the completion of the procedure, subject are dismissed from the registry after monitoring for post-procedure adverse device effects either at discharge or ≤48 hrs post-procedure, whichever is sooner.

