6.3. Screening (up to 30 days prior to index procedure)

This visit consists of screening and enrollment activities and may also include any pre-procedural planning in accordance with standard practice and local institution protocol. Subjects will be recruited from a pool of regular patient population that are eligible for percutaneous cardiac intervention procedure. This visit will consist of the following procedures.

Assessment of Eligibility

The Investigator will assess the subject's eligibility for this study per the inclusion and exclusion criteria listed in **Section 4.0** and will document the outcome of the eligibility assessment. If the subject qualifies, he or she will then undergo the registry-related imaging examinations described below. The investigator shall screen the patient and deem them suitable for conducting the procedure under conscious sedation.

Informed Consent

Study participation is voluntary. The potential subject if deemed eligible for the study based on the known information in the medical records, will be informed about the study and asked to participate. He/she will be given the most current IRB-approved Informed Consent Form (ICF) to read. Ample time will be provided for review and an opportunity to ask questions about the study. If the subject agrees to participate, they will sign the ICF and be given a copy of the signed document for their records. All components of the consent process will be documented in source documents. A detailed description of the consent process is provided in **Section 9.2**.

Medical History and Demographics

Standard subject demographics (e.g. age, gender, race, ethnicity, height, weight), relevant medical and surgical histories will be recorded. The assessments will be performed following the institutions' standard protocols and the results recorded on the appropriate subject case report forms. Any pertinent diagnostic imaging as it relates to the index procedure (e.g. CT, MRI, TTE) if performed per standard institutional protocol will be documented.

New information about the study

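### Section 4.5 relies on an eligibility decision at enrollment that no visit schedules and that Section 4.4 does not place before catheter insertion

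*Protocol*

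**What the plan says.** - **Exclusions.** Protocol Sections 1 and 4.2 list, among others, "Known contraindicated conditions include sepsis, major coagulation abnormalities, presence of any intracardiac thrombus", and also patients in whom placing the catheter is not technically feasible. The rule carries no time limit: "Patients who have ANY of the following exclusion criteria are NOT eligible for participation on the registry".
- **Schedule.** In Table 1 (Section 6.2), the row "Assessment of eligibility" has one mark, under Screening, which the footnote allows "up to 30 days prior to index". Section 6.4, on the index procedure, describes imaging and data capture and lists no eligibility step.
- **Enrollment.** Section 4.4: "A subject is considered enrolled in the registry when VeriSight has been placed in their vasculature", and the device has been switched on.
- **Screen failures.** Section 4.5: "Those who provide consent, but then are determined to be ineligible at the time of enrollment will be considered screen failures". The same section follows only subjects considered enrolled.
- **Analysis population.** Protocol Section 8.2, repeated in SAP Section 4.3, requires that no exclusion criterion is met. It gives the screen-failure label to people who consented but had no procedure with the Philips catheter.
- **Label.** Section 3.1: "Only on label uses of the VeriSight ICE catheter will be allowed".

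**The concern.** Section 4.5 depends on a decision that no visit in the protocol produces. The only scheduled assessment may be up to 30 days old by the procedure day. The only time point named for the later decision, enrollment, is defined by a device already in use.

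This matters because two exclusions can be recognised through the procedure itself:

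- **Technical feasibility.** An exclusion for placement that is not feasible overlaps with failure of technical success, which Section 3.2 defines partly by the catheter reaching its target position.
- **Intracardiac thrombus.** It is an exclusion, and Section 3.2 also gives thrombus as an example of a complication to be assessed under clinical success. Section 2.2 describes ICE as a way of detecting it.

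If eligibility has not been fixed and dated before insertion, the same finding can be counted as an outcome or recast as ineligibility, and that choice is made after the result is visible. At stake are the denominators of the three primary success proportions and the completeness of device-related safety follow-up.

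**Working it through.** No sample size, power or event count is involved, so the check sets the provisions side by side.

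**1. Count the scheduled checks.** Table 1 has one eligibility assessment at screening and none at the index procedure. Section 6 allows one to three visits, so screening may fall on the procedure day. The permitted interval is therefore 0 to 30 days.

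**2. Locate the decision that Section 4.5 uses.**

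| Provision | What it implies about timing |
|---|---|
| 3.3(c), SAP 4.5(c) | Eligibility is confirmed before inclusion; no interval or date is required |
| 6.3 | Qualifying at screening leads on to registry imaging; the visit is also said to include enrollment activities |
| 6.4 | No eligibility step |
| 4.4 | Enrollment is the point when the catheter is in the vasculature and on |
| 4.5 | Ineligibility may be determined at enrollment |

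Section 6.3 places enrollment activities at screening, while Section 4.4 places enrollment at insertion. Nothing puts the Section 4.5 decision on a particular side of insertion.

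**3. Trace one patient.** Suppose a patient passes screening, the catheter is placed and switched on, and the first images show an intracardiac thrombus judged to have been there already.

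- Section 4.4: enrolled. Under Section 7.7, collection of adverse device effects has started.
- Section 4.2: not eligible, since the exclusion is untimed.
- Section 4.5: a screen failure if this counts as determined at enrollment, and so not followed.
- Section 8.2, population sentence: outside the analysis population, because an exclusion is met.
- Section 8.2, screen-failure sentence: not a screen failure, because a procedure with the catheter took place.
- Section 1: all enrolled subjects are to be accounted for in the report, which does not settle the denominators.

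One patient thus receives incompatible classifications. SAP Section 8.2.1 plans neither an intention-to-treat nor a per-protocol analysis, so no second set exists in which such a patient would reappear.

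**4. Scale per patient.** This is arithmetic on the planned numbers, not an estimate of how often it happens. With one failure:

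- Final analysis: 199/200 = 99.5%; with that subject removed, 199/199 = 100%.
- Interim analysis: 99/100 = 99.0%; with that subject removed, 99/99 = 100%.

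The exact 95% intervals planned in SAP Section 8.7.1 would be computed on whichever denominator is chosen.

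**The case against.** The strongest reply is that the intent is clear. The exclusions are untimed, Section 3.3 wants eligibility confirmed before inclusion, Section 3.1 restricts use to the label, and Section 8.2 leaves out anyone meeting an exclusion. Table 1 is introduced as an overview, so a missing mark may be mere brevity. Section 4.5 need not mean the literal instant at which the device is switched on. Device use is directed by the treating team as standard care (Sections 2.4 and 6.4), with contraindications in the instructions for use.

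Most of this stands, and it rules out a stronger reading. A reader might infer that a patient contraindicated on the procedure day still qualifies, and that the registry therefore creates a safety gap. The documents do not support that: no rule admits such a patient, and nothing shows registry screening replacing the clinician's own check on the day. Nor are all the exclusions of rapid onset. Significant peripheral vascular disease is usually long-standing, and the documents do not discuss onset at all. A reader might also assume that 1% to 3% of patients become contraindicated in the interval and obtain 0.01 × 200 = 2 to 0.03 × 200 = 6 patients. Those rates have no source in the documents, and the sum assumes that nobody is recognised and cancelled before insertion.

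What the reply does not remove is the conflict over timing. Good intent does not date the check, and Sections 4.4, 4.5 and 8.2 still disagree about a patient found ineligible after the device is in use.

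**Conclusion.** The point holds as a conflict between sections and a check that is neither scheduled nor dated. It is not a finding that the plan enrolls contraindicated patients. Its size is one scheduled assessment at screening, none at the index procedure, and an interval of 0 to 30 days, where 30 is the maximum. The number of patients affected cannot be derived from the documents.

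The statistical consequence, possible removal of device-exposed subjects after results are known, rests on reading Sections 4.4, 4.5 and 8.2 literally and on a site or the sponsor applying them that way. Because the primary results are proportions from at most 200 subjects, even one such removal would be visible in the estimates. A correction is worth making, at moderate priority.

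**What to change.** Reconcile protocol Sections 4.4, 4.5, 6.2, 6.3, 6.4 and 8.2, and carry the result into SAP Section 4.3:

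1. In Table 1, add re-confirmation of eligibility to the Index procedure column. In Section 6.4, state that the existing criteria are re-confirmed from information already available, and dated, before VeriSight is inserted.
2. In Section 4.5, limit screen failures to patients found ineligible at or before that re-confirmation.
3. In Section 8.2 and SAP Section 4.3, keep everyone in whom the device was placed and switched on in the analysis population. Section 4.5 should keep them in follow-up. Ineligibility discovered later is recorded as a protocol deviation under Section 9.11.
4. In Section 6.3, align the reference to enrollment activities with Section 4.4.

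The cost is one dated eCRF field per subject and a few lines of text. No criterion, test or clinical rule changes. The re-confirmation will not reveal a condition that is silent until imaging, which is why items 2 and 3 matter at least as much as item 1: they settle in advance how such a patient is counted.

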2. INTRODUCTION

2.1. Device Description

Philips Image Guided Therapy Devices has recently developed and received FDA approval an intracardiac echocardiography (ICE) catheter (VeriSight/ VeriSight Pro, henceforth defined as VeriSight in this protocol) that has 2D and/or 3D imaging capabilities. These catheters are for use with Philips EPIQ series of ultrasound system. The indication for use for VeriSight is intended for intracardiac and intra-luminal visualization of cardiac and great vessel anatomy and physiology as well as visualization of other devices in the heart. The catheter is intended for imaging guidance only, not treatment delivery, during cardiac interventional percutaneous procedures. A detailed description of VeriSight can be found in the products' IFU.

The current benchmark for image guidance in percutaneous cardiac intervention procedure is transesophageal echocardiography. The major advantage of ICE over TEE is its unique imaging from within the heart, providing shorter image distances to target anatomy or device, and higher resolution. In addition, ICE can be used under conscious sedation thus avoiding the need of esophageal intubation and eliminating the risk for esophageal trauma. Further, ICE can also reduce fluoroscopy exposure to both the patient and the operator.

2.2. Background

ICE has been around for more than 20 years and its use has significantly increased with the advent of invasive electrophysiology (EP) and percutaneous structural heart disease (SHD) interventions. ICE is an advanced imaging modality that has become an integral part of a variety of percutaneous interventional and EP procedures, potentially improving outcomes and reducing risks¹⁻³.

Recent reports demonstrate that ICE utility as a primary guidance or as a supplement to transesophageal echocardiography (TEE) in various SHD and EP interventions such as left atrial appendage (LAA) closure, interatrial shunt closure, left and right heart transcatheter valve intervention, ventricular septal defect (VSD) and patent ductus arteriosus (PDA) closure⁴. There are several ultrasound imaging tools/techniques to guide cardiac interventions. Transthoracic echocardiography (TTE) was initially described to guide percutaneous interventions in 1984 by Kronzon et al. and offers a unique way to provide real time imaging^{4,5}. However, TTE is limited by shadow artifact from anterior structures, lower quality images from increased distances between the probe and heart, and image distortion from bone and lung tissue. The TTE probe over the chest wall also does not offer continuous procedural guidance and may disrupt the workflow during interventional procedures. TTE use during an intervention can be also problematic due to the need for a separate operator (a sonographer) to acquire and manipulate the images. TEE unlike TTE offers superior image resolution for left heart structures, and may allow visualization of the entire picture, including catheter tips, wires, and devices⁶. Drawbacks of TEE include the requirement for esophageal intubation and potential complications such as gastrointestinal tract injury, aspiration,

Document ID:	IGT_IGD_ICE Registry Study 2019 10745	Document title:		Classification:	Confidential
Modified:	24 APR 2021	Philips ICE Registry			
Version:	2.0	User Tool ID:	16.2.6UserTool0004		
Status:	Final	User Tool Version Date	30May2019	Page:	10

Clinical Registry Protocol

IGT_IGD_ICE Registry Study_2019_10745

and anesthetics side effects⁷. Additionally, anterior structures may be difficult to visualize on TEE secondary to far-field exposure and shadowing from adjacent structures. The probe may also obscure the interventionalists' field of view on fluoroscopy⁸.

The use of ICE avoids most of those limitations. As such, ICE has become a widely used ultrasound based imaging tool in the interventional laboratory. Imaging with ICE has evolved from cross-sectional imaging using a rotating transducer, to sector-based imaging using a phased-array transducer⁹. Phased array ICE has many advantages over rotational ICE including a greater frequency range, greater depth of field, steerability, and the possibility of acquiring Doppler and color flow imaging. Phased-array catheters can be easily advanced and positioned through short sheaths and do not require long guide sheaths. The major advantage of ICE over TEE is its unique imaging from within the heart, providing shorter image distances to target anatomy or device, and higher resolution. In addition, ICE can be used under conscious sedation thus avoiding the need of esophageal intubation and eliminating the risk for esophageal trauma. Further, ICE can reduce fluoroscopy exposure to both the patient and the operator¹⁰.

Evidence of Prior Clinical Data with ICE Technology

The performance and safety of the ICE imaging modality has been well established in different percutaneous interventions. Below we provide several examples of the outcomes of the utility of ICE technology in a variety of SHD and EP procedures.

Structural Heart diseases interventions

During transseptal catheterization, ICE helps provide direct visualization of the interatrial septum and is invaluable tool to guide a safe transseptal puncture. ICE delineates the anatomy of intra- and extracardiac structures not identified with fluoroscopy and simplifies correct positioning of the transseptal dilator, puncture of the fossa ovalis, and cannulation of the left atrium in a timely and uncomplicated fashion¹¹. In another study, the use of AcuNav ICE catheter during left heart radiofrequency ablation and transcatheter closure procedures successfully guided transseptal catheterization, provided imaging of normal or aberrant anatomy of the right/left atrial (interatrial septum, fossa ovalis, appendages, 4 pulmonary vein ostia) and right/left ventricular (valves and papillary muscles) structures. AcuNav was crucial in providing early identification of procedure complications, including pericardial effusion (n = 2, detected before systematic hemodynamic deterioration) and thrombus formation on sheaths deployed in the right atrium (n = 9) and left atrium (n = 2, early elimination with management of the sheath)¹².

Atrial Septal Defect Closure

Several studies have reported the feasibility and safety of ICE for guiding transcatheter closure of Atrial Septal Defect (ASD)³. There was close agreement between ICE and TEE in their assessment of device position and the adequacy of septal capture before device release (98%) and in identifying

Document ID:	IGT_IGD_ICE Registry Study_2019_10745	Document title:		Classification:	Confidential
Modified:	24 APR 2021	Philips ICE Registry			
Version:	2.0	User Tool ID:	16.2.6UserTool0004		
Status:	Final	User Tool Version Date	30May2019	Page:	11

Clinical Registry Protocol IGT_IGD_ICE Registry Study_2019_10745

the presence of significant residual shunts. ICE detected all potentially adverse events, including four malpositions, and guided appropriate remedial action^{13,14}.

Left Atrial Appendage (LAA) Imaging and Closure Procedures

ICE provides adequate visualization of the LAA and can be used as an alternative to TEE in guiding LAA occlusion (LAAO) procedures¹⁵⁻¹⁷. Matsuo et al. investigated a total of 27 patients with AF receiving Watchman left atrial appendage closure under ICE guidance at a single center. All patients were successfully implanted. There were no major procedural complications. The overall procedure-related complication rate was 14.8% primarily attributed to access site hematoma¹⁶.

Baseline clinical and procedural characteristics, and in-hospital outcomes were compared between patients in whom a Watchman was implanted with ICE vs. TEE guidance. Device implantation success rate was 100% in both groups. There were no device embolization, significant peri-device leak, tamponade, stroke, and access site bleeding reported in any patient. Total hospital stay for stand-alone LAAO was comparable between groups (2 days [2-2] vs. 2 days [2-3.3], P = 0.17, in ICE vs. TEE, respectively)¹⁷.

The impact of ICE to guide LAAO has been established¹⁵⁻¹⁸. Reported high technical success rates range between 96.7% and 100.0%, irrespective of RA or LA ICE probe position. Korsholm et al. studied the efficacy and safety of ICE and TEE from the left atrium for procedural guidance of transcatheter LAAO. Technical success was achieved in 99% of both the TEE and ICE group. Procedural success was 94.5% in ICE-guided group. Major peri-procedural complications occurred in 4.7% of the TEE group and 1.8% of the ICE group. In addition, contrast use and procedural time were reduced with ICE¹⁹.

Mitral Valve Procedures

ICE guidance for percutaneous catheter-based Mitral Valve (MV) repair techniques have been described. Saji et al. used ICE adjunctively with TEE for guiding percutaneous MV repair with the MitraClip system (Abbott Vascular) in patients with failed prior surgical rings. In this study, the ICE catheter was introduced transarterially into the LV and anteflexed to obtain a short-axis view of the valve. The authors state that ICE was helpful to assess the insertion of the posterior leaflet into the MitraClip's arms, particularly in this group of patients, in which TEE imaging of the MV may be shadowed by the surgical ring²⁰. During the MV Valvuloplasty procedure, ICE is used to rule out LAA thrombus, guide the transseptal catheterization, confirm optimal balloon position, monitor balloon inflation, and assess the valve before and after valvuloplasty^{21, 22}.

Transcatheter Aortic Valve Replacement (TAVR)

ICE-guided TAVR may represent an important alternative to TEE for TAVR imaging guidance and possibly allow for less-intensive sedation or anesthesia²³. Other advantages of ICE include

Document ID:	IGT_IGD_ICE Registry Study 2019 10745	Document title:		Classification:	Confidential
Modified:	24 APR 2021	Philips ICE Registry			
Version:	2.0	User Tool ID:	16.2.6UserTool0004		
Status:	Final	User Tool Version Date	30May2019	Page:	12

Clinical Registry Protocol

IGT_IGD_ICE Registry Study_2019_10745

uninterrupted monitoring, no fluoroscopic interference, and precise Doppler-based assessment of pulmonary artery pressures²⁴.

Electrophysiology procedures

The EP procedure involves study and treatment of rhythm disorders of the heart. There are several therapeutic and surgical methods to treat many of the rhythm disturbances of the heart such as surgical implantation of pacemakers and implantable cardioverter–defibrillator.

ICE can be used in AF ablation procedures to guide transseptal puncture. ICE imaging can also be used in the following procedural steps, including (1) characterization of pulmonary vein anatomy (number of veins, diameter, anatomic variants), (2) transseptal catheterization, (3) catheter positioning and contact monitoring, (4) assessment of lesion formation, (5) prevention and early detection of procedural complications such as pericardial effusion or thrombus formation, (6) assessment of pulmonary veins physiology/flow before and after ablation, and (7) location of the esophagus in relationship to the pulmonary vein ostium^{25, 26}. ICE is useful to assist ablation of the cavotricuspid isthmus (CTI) in patients with typical atrial flutter. In a randomized trial that included 102 patients with typical flutter, ICE-guided ablation of the CTI significantly shortened the procedure time radiation exposure, and time spent for ablation in comparison with fluoroscopy-only procedures. About 13% of the patients from the fluoroscopy-only group crossed over to ICE guidance because of failure to achieve CTI block and were all treated successfully²⁷.

ICE has an invaluable role in the mapping and ablation of ventricular arrhythmias. It provides real-time visualization of the ablation catheter in relation to a particular anatomic structure, allowing for continuous assessment of catheter–tissue contact. This is key for effective energy delivery to the targeted structure of interest, possibly increasing effectiveness and limiting collateral damage. Lesion formation is typically visualized in ventricular tissue as the development of increased echogenicity during ablation²⁸. Saksena et al. studied the role of ViewFlex ICE catheter in comparison to TEE in imaging of left atrium and interatrial septal during atrial fibrillation. ICE and TEE showed concordance for LAA, IAS and SEC imaging but not for LA and LAA thrombus detection where ICE imaging was less sensitive compared to TEE for LAA thrombus identification. There were no adverse events or complications reported for ICE or TEE²⁹.

Transvenous Lead Extraction

Sadek et al. reported the utility of ICE during transvenous lead extraction. ICE imaging provides continuous monitoring for procedural complications. It allows for identification of lead binding sites within the heart or the SVC, which are predictive of a more complex procedure and the need for advanced extraction tools. In addition, ICE can detect the presence of lead-related echo densities, suggestive of thrombi or vegetations. Interestingly, these echo densities were found in 72% of patients, mostly in the absence of bacteremia³⁰.

Document ID:	IGT_IGD_ICE Registry Study 2019 10745	Document title:		Classification:	Confidential
Modified:	24 APR 2021	Philips ICE Registry			
Version:	2.0	User Tool ID:	16.2.6UserTool0004	Page:	13
Status:	Final	User Tool Version Date	30May2019		

